9.4.3 ANALYSIS OF THE SECONDARY ENDPOINT(S)

SECONDARY END POINT: AUC Serum creatinine over 10 days adjusted for baseline serum creatinine

We expect that rate of change in AUC serum creatine will be decreased in the NR group relative to the Placebo group. The null hypothesis to be tested is $H_0:R_{NR}=R_{Placebo}$, where R_{NR} and $R_{Placebo}$ are the rates of change in serum creatinine from baseline to day 10 in the NR and Placebo arms. Serum creatinine will be measured daily in each patient during the first 10 days upon randomization. Serum creatinine AUC will be graphically summarized with spaghetti plots and overlaid line and whisker plots of the mean trajectory for each arm with the whiskers being of length equal to one standard error of the mean. To address non-ignorable missingness due to dialysis, death, or withdrawal of consent, all of which may be considered as informative censoring, the statistical method will be the same as that specified for NAD+. Potential participants who may have severe AKI or advanced CKD will considered with a binary independent variable in the models addressing this condition with corresponding displays of the line and whisker plots by treatment group and summary tables of coefficients, standard errors and p-values. Interactions between this binary variable and treatment will be of interest and will be described.

SECONDARY END POINT: Serum creatinine AUC and ordinal categorical outcome with four categories including dialysis and death

Serum creatinine AUC will be computed using the trapezoidal rule within each patient starting from randomization to day 10, and will be assigned to Category 1 if AUC < median AUC, to Category 2 if AUC \geq median AUC in those who do not experience dialysis and who do not die during the first 10 days of hospitalization. Patients who experience dialysis at any time during the 10 day period will be assigned to the Category 3 and those who die during the first 10 days of hospitalization to Category 4. The null hypothesis is H₀: OR₁=OR₂=OR₃=1, where OR₁, OR₂, and OR₃ are the odds ratios for Categories 1, 2, 3, and 4. If the proportional odds model holds the null hypothesis is H₀:OR=1 where OR is the single odds ratio summarizing the treatment effect. With NR treatment we expect that the odds of Category 1 will be increased, the odds of Category 2, 3, and 4 will be decreased.

The primary analysis will be based on a cumulative logit model for ordinal data of the primary outcome with terms for treatment, age, gender, clinical site, and baseline serum creatinine. The proportional odds assumption will be tested with a score statistic and empirical logit plots. If the proportional odds assumption is violated then the analysis will be conducted under a partial proportional odds assumption. Under a partial proportional odds assumption, three odds ratios will be estimated; if evidence suggests that the proportional odds assumption holds, a single odds ratio will summarize the treatment effect. In either case, the odds ratio estimate(s), 95% confidence interval(s), and p-value(s) will be reported. Further study will be indicated if the p-value for any treatment effect suggesting benefit in the NR arm is less than or equal to 0.05.

SECONDARY END POINT: Major Adverse Kidney Events (MAKE)

The null hypothesis is H₀:HR=1 where HR is the ratio of the hazard of MAKE with NR treatment to the hazard of MAKE with Placebo treatment. We expect that HR will be less than 1. MAKE is defined as Yes if a doubling of serum creatinine (from baseline), the initiation of long-term dialysis, or death from any cause is observed, and No otherwise. Treatment arms will be compared with regard to the time to the first occurrence of MAKE over the entire duration of the study from baseline to 90 days post-randomization with proportional hazard models of time to MAKE in terms of treatment without and with adjustment for age, race, clinical site, baseline

serum creatine. The coefficients, standard errors and 95% confidence intervals and corresponding hazard ratios will be reported without and with adjustment for covariates. The proportional hazards assumption will be assessed with Schoenfeld residuals and log survival plots. The unadjusted model will be graphically summarized with overlaid Kaplan Meier curves and the p-value for the corresponding log rank test. Covariate interactions with treatment will be of interest and will be explored.

SECONDARY END POINT: Kidney impairment as indicated by eGFR and proteinuria at 30 and 90 days

The null hypothesis to be tested is H_o : $R_{NR}=R_{Placebo}$, where R_{NR} and $R_{Placebo}$ are the mean rates of change of eGFR in patients randomized to NR or to Placebo respectively from baseline to day 30 and day 90. We expect the eGFR rate of change to be increased with NR relative to Placebo. The same hypothesis will be tested for proteinuria, using log-transformed urinary albumin-to-creatinine ratio, where we expect the mean proteinuria rate of change to be decreased with NR relative to Placebo.

We will quantify kidney dysfunction at 30 days and 90 days post-randomization, measured by eGFR calculated by the CKD-EPI (the Chronic Kidney Disease Epidemiology Collaboration) equation [87] and the urine protein/creatinine ratio (PCR). To address non-ignorable missingness due to dialysis, death, or withdrawal of consent, all of which may be considered as informative censoring, the statistical method will be the same as that specified for NAD+.

eGFR will be evaluated untransformed, while urine PCR will be log-transformed to evaluate percent change because urine PCR is highly skewed and relative changes in urine PCR are proportional to risk of adverse renal and cardiovascular outcomes. We will include time, treatment, and interactions of treatment with time as independent variables in a mixed effects linear model. We will focus on the coefficient for the interaction of treatment with time as the primary measure of treatment effect. We will consider a p-value <0.05 for this interaction term to indicate a significant treatment effect. These analyses will be further adjusted for baseline characteristics that are prognostic of the outcome, including age, sex, clinical site, and stage of AKI at randomization. Adjustment will be accomplished by adding covariates and interactions of covariates with time.

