1 PROTOCOL SUMMARY

1.1 SYNOPSIS

Title	NIcotinamide Riboside in SARS-CoV-2 pAtients for reNAl protection (NIRVANA)			
Study Description	A pilot, double-blind, placebo-controlled, multicenter, interventional clinical trial with oral nicotinamide riboside (NR) 500 mg (versus placebo) twice daily for a total of 10 days in hospitalized participants with COVID-19.			
Objectives	Primary			
	 To determine the effect of nicotinamide riboside (NR) on whole blood NAD+ levels in hospitalized patients with COVID-19 infection and AKI during the 10-day intervention period; To evaluate the safety of NR in patients with COVID-19 infection and AKI during the 10-day intervention period; 			
	Secondary			
	 To determine the effect of NR on changes in area under curve (AUC) serum creatinine from baseline during the 10-day intervention; To determine the effects of NR on serum creatinine AUC, dialysis, and death with an ordinal categorical outcome having four categories (labeled 1, 2, 3, 4), defined as, in order from least to most severe disease, 1. Serum creatinine AUC < median, 2. Serum creatinine AUC ≥ median, 3. Dialysis, 4. Death during the 90d period post randomization; To determine the effect of NR on MAKE (Major Adverse Kidney Events; composite criteria defined as development or progression of chronic kidney disease, the initiation of long-term dialysis, or death from any cause) at 30d and 90d post randomization; To determine the effect of NR on degree of kidney impairment defined with estimated glomerular filtration rate (eGFR) and proteinuria at 30d and 90d post randomization; 			
	Exploratory			
	• To determine the relationship of whole blood NAD+ levels with AUC creatinine and surrogate markers of AKI such as kidney injury molecule- 1 (KIM-1) and neutrophil gelatinase-associated lipocalin (NGAL);			
Endpoints	Primary			
	 Rates of change in whole blood NAD+ level from baseline to day 10 in NR compared to Placebo. Safety of NR in hospitalized patients with COVID-19 and AKI (defined as the occurrence of at least one serious adverse event of grade 3 or higher or the occurrence of thrombocytopenia (>25% decline in blood platelet count from baseline value). 			

	Secondary				
	 Rates of change in AUC serum creatinine benchmarked to baseline from baseline to day 10 in NR compared to Placebo; An ordinal categorical outcome with four categories (labeled 1, 2, 3, 				

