We also plan to assess the AUC of serum creatinine benchmarked to baseline and other clinical outcomes as secondary endpoints to determine if there are trends indicating that NR may be a promising treatment for hospitalized COVID-19 infected patients who develop AKI. We will also correlate whole blood NAD+ levels with AUC creatinine with well described surrogate markers of AKI (KIM-1, NGAL) as an exploratory outcome measure. If we demonstrate that NR increases whole blood NAD+ in COVID-19 positive patients with AKI and is safe, this result would be a compelling finding to support further clinical trials with NR in this population. Further support for future studies would be obtained from our secondary endpoints and will of great value in establishing power calculations for future definitive studies [9, 10].

Upon completion of the NRIVANA study, we plan to pursue a Phase IIb or Phase III study based on the following scenarios:

- 1. Demonstrate significant increase in whole blood NAD+ level in the NR group compared to placebo (p<0.05), no significant increase in harm with NR treatment and a positive trend or improvement in any one of the secondary outcomes (p<0.2) would warrant a future Phase III study.
- 2. Demonstrate significant increase in whole blood NAD+ level in the NR group compared to placebo (p<0.05) and no significant increase in harm with NR treatment would warrant a Phase IIb study.
- 3. Demonstrate significant improvement in any one of the secondary outcomes with NR compared to placebo (p<0.2) and no significant increase in harm with NR treatment would warrant a Phase IIb study.

In a future Phase III clinical trial, we envision the primary endpoint would be the MAKE (Major Adverse Kidney Events) – the proportion of subjects who develop any of the components of MAKE at d90 post randomization. In the NIRVANA study MAKE is one of the secondary endpoints.

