Daily serum creatinine: Blood will be collected daily for the measurement of serum creatinine and documented for the study starting Day 1 and up to 10 days of hospitalization for participants who remain hospitalized or via StatSensor Xpress[®] for creatinine and outpatient serum creatinine measurement for participants who will be discharged prior to the 10-day intervention period. There will be a serum creatinine measured on the 10th day for discharged participants, in addition to the StatSensor Xpress[®] fingerstick creatinine measurement. AUC will be computed cumulatively across days for each patient.

Daily urine output: Daily urine output will be reported as part of routine clinical care and documented for the study starting Day 1 and up to 10 days of hospitalization. Daily urine outputs will not be obtained for participants who will be discharged prior to 10-day intervention period.

Onset of dialysis: Timing of onset of dialysis will be reported as part of routine clinical care and documented for the study starting Day 1 and up to 10 days of hospitalization.

Research Laboratory Biospecimens Collections for future Biomarkers Analysis:

Blood and urine will be collected at Visit 1 and then every visit thereafter for secondary or substudy analyses. Baseline (Day 1) blood and urine collections will be performed before participants receive first study drug dosing and after obtaining consent. There will be additional blood and urine collections on Day 1 at hour 3 and hour 6 after first drug administration for pharmacokinetics and analyses of biomarkers. Day 1 to Day 10 blood and urine collections will coincide with routine collection by the hospital staff. Hospital laboratory will aliquot and store the specimens and they will be picked up by the study team for storage in a COVID-19 designated biorepository. Each day, participants will collect first morning void urine into a provided container which will be kept refrigerated and picked up daily (until Day 9) by the courier service for delivery to the hospital laboratory. At Day 10, the study team will visit the participant at home to collect blood and first morning void urine and will deliver to the hospital laboratory. Both blood and urine biospecimens will be aliquoted and stored at the hospital laboratory by the hospital staff and will be picked up by the study team for storage in the COVID-19 designated biorepository at UTHSA. The list of research laboratory tests is provided in Table 4.

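### The creatinine AUC endpoint has a null hypothesis on creatinine itself, no formula for benchmarking to baseline, and no listed model term that would adjust its slope for baseline

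*Combined protocol and SAP*

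**What the plan says.** Three descriptions of the endpoint agree that it is an AUC related to baseline. The synopsis (1.1) lists "Rates of change in AUC serum creatinine benchmarked to baseline from baseline to day 10 in NR compared to Placebo", and Table 2 in Section 3 has the same endpoint in shorter form. The rationale (2.1) says "We also plan to assess the AUC of serum creatinine benchmarked to baseline and other clinical outcomes as secondary endpoints". The heading in 9.4.3 is "AUC Serum creatinine over 10 days adjusted for baseline serum creatinine".

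Under that heading, the expected direction is "We expect that rate of change in AUC serum creatine will be decreased in the NR group relative to the Placebo group", and the display is also of AUC: "Serum creatinine AUC will be graphically summarized with spaghetti plots". The null hypothesis between them equates two rates that "are the rates of change in serum creatinine from baseline to day 10 in the NR and Placebo arms".

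On construction, 8.1 says "AUC will be computed cumulatively across days for each patient". The trapezoidal rule appears only under the ordinal endpoint: "Serum creatinine AUC will be computed using the trapezoidal rule within each patient starting from randomization to day 10".

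The method is taken over from the NAD+ analysis in 9.4.2. There the contrast is the slope on day by treatment. The unadjusted model has no baseline creatinine. The adjusted model lists age, race, site, baseline creatinine, treatment and day. For eGFR and proteinuria, later in 9.4.3, adjustment explicitly includes covariate-by-time interactions. No such statement is made for AUC.

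**The concern.** The null hypothesis defines the test, and here it names a different variable from the endpoint. A creatinine slope measures direction of travel over ten days. An AUC measures how high creatinine was and for how long, which is the reason Section 3 gives for using it. An analyst following the null hypothesis and one following the heading would test different things.

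Putting AUC back does not settle what is tested, because raw, Day-1-subtracted and covariate-adjusted AUC are all still open. If raw AUC is analysed with the terms listed in 9.4.2, the adjustment promised in the heading does not reach the slope contrast.

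This is one secondary endpoint in a study that 9.4.1 calls exploratory. It can still matter for planning: in 2.1, p<0.2 on any one secondary outcome can support a further trial, provided there is no significant increase in harm (and, for Phase III, a significant NAD+ result).

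**Working it through.** The plan gives no creatinine mean, SD, course or power, so there is no figure to reproduce. From the documents I take Days 1 to 10, cumulative trapezoidal AUC, a slope contrast, two-sided 5%, and 40 per arm (the number used for NAD+ in 9.2). Everything else below is assumed.

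**1. What the slope of a cumulative AUC measures.** The least-squares slope on day has Sxx = 82.5. Applied to the cumulative trapezoid, it weights Days 1 to 10 by 0.027, 0.076, 0.112, 0.136, 0.148, 0.148, 0.136, 0.112, 0.076, 0.027 (sum 1.0). It is a weighted mean of daily creatinine, that is, a level. An arm flat at 3.0 and an arm flat at 2.0 both have creatinine slope 0, but their raw AUC slopes differ by 1.0.

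**2. When the two null hypotheses agree.** For a linear course, AUC minus baseline × T equals slope × T²/2, with T = 9. A slope difference of 0.10 per day gives 0.10 × 81/2 = 4.05, so the direction agrees. For a course that rises by 1 and returns along a parabola, against a flat arm, the creatinine slope difference is 0 while the AUC above baseline differs by (4/81) × Σk(9−k) over k = 1 to 8 = (4/81) × 120 = 5.93.

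**3. Can they favour opposite arms?** Let arm B go linearly from 2.5 to 2.8: creatinine slope +0.033 per day, Day-1-subtracted AUC slope 0.15. Let arm A go from 2.5 to 4.0 on Day 5 and then fall.

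| Arm A on Day 10 | Arm A creatinine slope | Arm B creatinine slope | Opposite directions? |
|---|---|---|---|
| 2.3 | −0.037 | +0.033 | yes |
| 2.8 | +0.021 | +0.033 | yes |
| 3.0 | +0.044 | +0.033 | no |

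With arm A ending at 2.3, its subtracted AUC slope is 0.83 against 0.15, clearly worse. At that end value and a Day 5 peak, the reversal holds for peaks of 3.0 to 4.0 but not at 2.75 or lower. With peak 4.0 it holds for peak Days 2 to 7 but not Day 8.

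**4. Does a baseline main effect adjust the slope?** In 1,000 simulated trials per scenario (daily creatinine as outcome, fixed-covariance GLS, complete data), adding baseline as a main effect changed the day-by-treatment estimate by at most about 2e-15. With 27–28% of participants truncated early, the mean shift was 0.0004 to 0.003 and the SD did not fall. A baseline-by-day term, with complete data, lowered the SD from 0.0131 to 0.012 (weak baseline–slope link) or from 0.0186 to 0.012 (stronger link).

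**5. Size of the precision cost.** Assumed: mean 2.5, between-subject SD 0.8, slope SD 0.1 per day, residual SD 0.2, slope difference 0.07 per day. The mean day exceeds Day 1 by 4.5, so the AUC-slope effect is 0.07 × 4.5 = 0.315.

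- Raw AUC slope: variance 0.8² + 4.5² × 0.1² + 0.2² × 0.119 = 0.847, where 0.119 is the sum of squared weights. SD of the arm difference = √(2/40 × 0.847) = 0.206, and 0.315/0.206 = 1.53.
- Day 1 subtracted: the level cancels. Variance 0.2025 + 0.04 × 1.065 = 0.245, SD √(0.05 × 0.245) = 0.111, and 0.315/0.111 = 2.84.
- Creatinine slope: SD √(0.05 × (0.01 + 0.04/82.5)) = 0.0229, and 0.07/0.0229 = 3.06.

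Simulated power (8,000 trials) is 0.33, 0.81 and 0.86 respectively. Raw AUC slope regressed on arm and Day 1 creatinine, which is equivalent to a baseline-by-day term, also gives 0.81. Null rejection is 0.048 to 0.053 throughout.

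Over between-subject SD 0.4–1.2, slope SD 0.05–0.2 and residual SD 0.1–0.3 (27 combinations), raw AUC has power 0.14–0.86, baseline-adjusted AUC 0.30–1.00, and the gain is 0.02 to 0.80. The gain is smallest with slope SD 0.2 and between-subject SD 0.4.

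**The case against.** The mismatch looks editorial. Every other statement of this endpoint names AUC, so a sensible analyst would restore the word. That is fair, and it shows which family of quantity is meant. It does not say whether AUC is raw, subtracted or covariate-adjusted.

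The variable list in 9.4.2 is not a full term specification. It omits day by treatment as well, although the same models are to supply slope contrasts. A reader might infer that the plan rules out a baseline-by-day term. The text supports only that none is stated.

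The power of 0.33 belongs to the least favourable reading. Someone who reads benchmarking as subtracting Day 1 already has 0.81, and the null hypothesis as written has 0.86, slightly above the proposed repair. A reader might take 0.33 as this trial's power. The documents do not support that, because every variance behind it is assumed.

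A reader might also infer that the unadjusted contrast is biased. It is not confounded by baseline, since allocation is randomized. Nor do the two measures generally point in opposite directions: linear courses agree, and the example stops reversing once arm A ends at 3.0.

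**Conclusion.** The point holds as a specification gap. The null hypothesis and the endpoint name different quantities, benchmarking is undefined, and the listed model does not deliver the baseline adjustment in the heading. The main-effect result is exact with complete data and approximate with dropout. The cost in power depends on unknown creatinine variances and runs from negligible to large. Opposite conclusions require a rise-and-fall course with a low enough end value. The censoring part of the planned method and the fingerstick values were not simulated. The change should be made, in proportion to one secondary endpoint that can feed the p<0.2 planning scenarios.

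**What to change.** In 9.4.3, for this endpoint only, choose one definition and state the null hypothesis on it:

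- equal mean rate of change, Day 1 to Day 10, of the cumulative trapezoidal AUC of creatinine minus Day 1 creatinine; or
- the same for raw cumulative AUC, with baseline creatinine and baseline creatinine by day in the main model.

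Use the chosen wording in 1.1, 2.1 and Table 2. Keep the informative-censoring method. Wherever baseline creatinine is meant to adjust the slope, add its interaction with day. The eGFR and proteinuria text is precedent for covariate-by-time terms in general, but the covariates it names are age, sex, site and AKI stage, not baseline creatinine.

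Leave the general AUC computation in 8.1, the ordinal endpoint and the correlations in 9.4.9 as they are. A subtracted formula placed in 8.1 would redefine those as well.

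The cost is a few sentences and, where the interaction is used, one more model parameter. Day 1 and daily creatinine are already collected.

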 baseline during the 10-day intervention; To determine the effect of NR on serum AUC, dialysis, and death with an ordinal categorical outcome with four categories (labeled 1, 2, 3, 4), defined as, in order from least to most severe disease, 1. Serum creatinine AUC < median, 2. Serum creatinine AUC ≥ median, 3. Dialysis, 4. Death; To evaluate the effect of NR on on MAKE (composite criteria defined as development or progression of chronic kidney disease), the initiation of long-term dialysis, or death from any cause) at 30d and 90d post randomization. To determine the effect of NR on kidney function defined by eGFR and proteinuria at 30d and 90d post randomization. 	 outcome with four categories (labeled 1, 2, 3, 4), defined as, in order from least to most severe disease, 1. Serum creatinine AUC in the first tertile, 2. Serum creatinine AUC in the second tertile, 3. Serum creatinine AUC in the third tertile, 4. Death; Time to first occurrence of MAKE defined as doubling of serum creatinine, the initiation of long-term dialysis, or death from any cause at 30 day and 90 day post randomization; Kidney function defined by estimated glomerular filtration rate (eGFR) and proteinuria at 30d and 90d post randomization. 	 days of intervention and benchmarked to baseline, has been linked to reduced progression of chronic kidney disease (CKD). The ordinal categories address the hierarchy of increase in severity as has been used in recent COVID-19 studies as per the World Health Organization clinical progression scale [57, 58] AKI may progress to CKD which is associated with need for dialysis and increased mortality.
• To determine the relationship of whole blood NAD+ levels with AUC creatinine and surrogate markers of AKI such as kidney injury molecule-1 (KIM-1) and neutrophil gelatinase- associated lipocalin (NGAL);	• Correlations between whole blood NAD+, AUC serum creatinine, and surrogate markers of AKI such KIM1 and NGAL;	 AUC of serum creatinine is a direct assessment of the duration and severity of AKI; KIM-1 and NGAL are promising surrogate urinary biomarkers of AKI however, their clinical utility in COVID-19 patients with AKI is not known;

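### The ordinal kidney outcome splits a continuous creatinine AUC at the median, which costs this endpoint power for an effect on AUC; its definition also differs between sections

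*Combined protocol and SAP*

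**What the plan says.** Section 9.4.3 computes each patient's creatinine AUC by the trapezoidal rule from randomization to Day 10. Among patients with neither dialysis nor death, a patient "will be assigned to Category 1 if AUC < median AUC" and otherwise to Category 2. Above these, "Patients who experience dialysis at any time during the 10 day period will be assigned to the Category 3", and deaths form Category 4. The section does not say whether the median is pooled over the arms, but one common median is the natural reading.

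On the model: "The primary analysis will be based on a cumulative logit model for ordinal data of the primary outcome". Besides the treatment term, it adjusts for baseline creatinine, site, gender and age. Despite that wording, the outcome is listed as secondary in the Synopsis, in Table 2 and in the 9.4.3 heading. Proportional odds is to be checked by a score test, with a partial proportional odds model giving three odds ratios as the fallback.

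The definition is not the same everywhere:

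| Place | AUC levels | Dialysis level | Window |
|---|---|---|---|
| Synopsis (1.1), objective | two, cut at the median | yes | 90 days |
| Table 2, objective column | two, cut at the median | yes | not given |
| Table 2, endpoint column | three, up to "Serum creatinine AUC in the third tertile" | none | not given |
| 9.4.3 | two, cut at the median | yes | 10 days |

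Table 2 gives this rationale: "The ordinal categories address the hierarchy of increase in severity as has been used in recent COVID-19 studies". Section 9.4.3 also has a separate secondary endpoint, the rate of change in creatinine AUC, analysed without categories.

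**The concern.** The plan measures a continuous quantity and then keeps only which side of the sample median it falls on, for what is probably the large majority of patients. Differences between patients on the same side no longer count. The AUC being cut is, as written, the total AUC and not one benchmarked to baseline. Creatinine at entry therefore does much to decide the side, and the model then adjusts for baseline creatinine. That leaves the treatment term relying mainly on patients near the cut.

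The rationale in Table 2 supports a hierarchy of kidney function, then dialysis, then death. It does not call for a median cut inside the mildest group.

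The p-value is used in decisions. Section 9.4.3 ties further study to p ≤ 0.05 on this outcome. Section 2.1 lets any one secondary outcome at p < 0.2 help choose between a Phase III and a Phase IIb study, or support a Phase IIb study without a NAD+ effect. No other endpoint ranks graded creatinine, dialysis and death together.

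**Working it through.** **Inputs from the documents.** 100 randomized 1:1, so 50 per arm (5.5, 6.1.1). Two-sided 5% (9.4.1). Withdrawal of 15% plus 5% attrition (5.5), leaving about 40 per arm. Mortality 9.9%, dates unknown (2.2). **Assumed, because the documents are silent:** the AUC effect d in SD units, normally distributed AUC, the dialysis rate, the 10-day death rate, and the correlation of baseline creatinine with AUC.

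**1. The plan's own figure.** Section 9.2 covers NAD+ only. SD of change = 10 × √(2 × (1 − 0.5)) = 10. With n = 40 and d = 2.1, power exceeds 99.9%. The minimum detectable effect is (1.960 + 0.842) × √(2/40) = 0.626, or 0.63 (at 80% power, which the plan does not state). Both figures reproduce. No power figure is given for the ordinal outcome.

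**2. Hand check in event-free patients.** With 15% events, 50 × 0.85 = 42.5, so take n = 42 per arm and d = 0.5.
- Uncut AUC: Φ(d√(n/2) − 1.96) = Φ(2.291 − 1.960) = 63.0%.
- Median split: the proportions are Φ(±0.25) = 0.599 and 0.401, a difference of 0.1974. The null SE is √(0.5/42) = 0.1091 and the alternative SE is √(2 × 0.599 × 0.401/42) = 0.1070. Power = Φ((0.1974 − 1.96 × 0.1091)/0.1070) = Φ(−0.154) = 43.9%.
- Loss: 19 points. At d = 0.3 it is 27.9% against 19.1%, or 9 points. Over n = 34 to 50 and d = 0.3 to 0.7 the loss is 7 to 21 points.

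**3. Whole outcome, unadjusted.** Tie-corrected rank test, 20,000 simulated trials per row, 50 per arm, effect on AUC only. Full ranks means event-free patients ordered by AUC, then dialysis, then death. The tertile column keeps dialysis and death as levels above the tertiles.

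| Dialysis / death | d | Median split | Tertiles | Full ranks | Loss |
|---|---|---|---|---|---|
| 5% / 5% | 0.3 | 15.0% | 18.4% | 21.6% | 6.6 |
| 5% / 5% | 0.5 | 33.5% | 42.2% | 49.5% | 16.0 |
| 10% / 9.9% | 0.3 | 10.9% | 13.0% | 15.2% | 4.3 |
| 10% / 9.9% | 0.5 | 21.8% | 27.4% | 33.3% | 11.5 |
| 20% / 9.9% | 0.3 | 8.3% | 9.5% | 10.7% | 2.4 |
| 20% / 9.9% | 0.5 | 14.2% | 18.1% | 21.8% | 7.6 |

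Rejection under the null was 4.8 to 5.2% for all three scorings.

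**4. Whole outcome, cumulative logit with baseline creatinine.** 50 per arm, death 5%, dialysis 10%, effect of 0.5 conditional SD on AUC only, 2,000 trials per row.

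| Baseline–AUC correlation | Median split | Full ranks | Loss |
|---|---|---|---|
| 0 | 26% | 40% | 14 |
| 0.5 | 24% | 42% | 18 |
| 0.7 | 20% | 41% | 21 |

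Repeat simulations with 400 and 500 trials per cell gave losses of 16 to 22 points. Absolute power differed between runs by more than simulation error in places, so the loss is best read as a range. Rejection under the null was about 4.4 to 6.4% for both scorings.

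Smaller effects: at 0.3 SD, 13% against 20%. At 0.3 SD with 30% of patients having events, 7% against 11% in one run and 9% against 14% in another. At 0.3 SD with 40 per arm, 10% against 15%.

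**5. At p < 0.2.** 0.5 SD, 50 per arm, correlations 0, 0.5 and 0.7: 57% against 71%, 54% against 73%, 45% against 72%. Across the cases run the loss was about 8 to 27 points.

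**6. Effects on the events.** If NR affects only dialysis and death, full ranks lose 2 to 3 points at power near 14%. If events are also reduced (risk ratio 0.6, d = 0.5, dialysis 10%, death 5%, unadjusted), power is 53.4% against 67.8%.

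**The case against.** Five points on the other side carry weight.

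- **The trial already tests AUC uncut.** A reader might infer that a kidney benefit would be missed because of the cut. The documents do not support that. Section 9.4.3 states, for a separate endpoint, "We expect that rate of change in AUC serum creatine will be decreased in the NR group relative to the Placebo group". A simple stand-in for that test, ANCOVA of AUC in event-free patients (0.5 SD, correlation 0.5), had 67% power, against 46% for full ranks and 24% for the split. The cost is to the ordinal endpoint alone. What remains is that the separate endpoint treats dialysis and death as informative censoring and does not rank them as worse. MAKE counts creatinine only if it doubles and dialysis only if long-term.
- **No fixed figure is available.** A reader might take a loss of around 20 points as a property of the plan. It is not: it shrinks with smaller effects and more events, and reverses slightly if only dialysis or death is affected.
- **Table 2 uses tertiles.** In the unadjusted runs, tertiles recover about half the loss. That column drops dialysis, however, so it conflicts with 9.4.3 and does not remedy it.
- **The fallback does not carry over.** An effect on AUC alone violates proportional odds. With 85 distinct AUC values plus dialysis and death there are 87 levels. Six covariate terms would give the score test 85 × 6 = 510 degrees of freedom from 100 patients. This stands, and the fix has to deal with it. The partial proportional odds model was not simulated.
- **The study is exploratory.** Section 9.4.1 says so, no power is claimed for this outcome, and no stated figure is wrong. That limits the severity, but the p-value still enters two decision rules.

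**Conclusion.** The concern holds for this endpoint and is conditional in size. For an effect on AUC alone, with 50 per arm, two-sided 5%, baseline creatinine in the model, 5% deaths and 10% dialysis, the median split costs about 14 to 22 points of power at 0.5 SD and about 7 at 0.3 SD. At 0.3 SD with 20 to 30% events it costs about 2 to 5 points. These effect sizes, event rates and the AUC distribution are assumptions. That event-free patients are most of the sample is likely from the 9.9% mortality, but it also depends on the unstated dialysis rate. The lenient p < 0.2 rule does not remove the loss. The plan should be changed on this point, but the change is an efficiency gain on a secondary outcome and does not correct an invalid analysis.

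**What to change.** 1. Reconcile the outcome first. The Synopsis, both columns of Table 2 and 9.4.3 should give one definition: the same levels, dialysis included or not, and one window (90 or 10 days).
2. In 9.4.3, keep the hierarchy but rank patients free of dialysis and death by their actual 10-day AUC, with dialysis next and death worst. Fit the same cumulative logit model with the planned covariates. Report one treatment odds ratio with its 95% CI.
3. For this ranked analysis, drop the score test and the partial proportional odds fallback. State in advance that the single odds ratio is the average summary whether or not the odds are proportional. Restate the null hypothesis as OR = 1.
4. Keep the four-category table, with its cut-specific odds ratios, as a supportive display of any non-proportionality.

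Cost: amended wording in three places, with no new data or visits and the same model class. The downsides are a less familiar odds ratio, a changed fallback, and a few points of power lost if NR acts only on dialysis or death.
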